#### 4.2. Description of the trial design.

Open Multicentre Randomized Controlled Trial, in parallel groups, based on treatment with progesterone comparing the placement of a prophylactic cervical pessary with usual management in singleton pregnancies at high-risk of PTB due to a history of at least one previous preterm delivery and/or a history of late abortion.

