## **7. Statistics**

### **7.1. Description of statistical methods.**

A descriptive analysis by preterm birth will be carried out calculating means and medians for quantitative variables and proportions for categorical variables.

Two-sided Z-tests will be used for comparing among exposure and outcomes groups per pregnancy. A multivariate logistic regression will be fitted to control for possible confounders. Relative risks and 95% confidence interval will be calculated for the outcomes.

All analysis will be carried out with SPSS® 19.0 statistical package (IBM Company SPSS Inc. Headquarters, Chicago, Illinois. USA). Statistical significance will be accepted in all cases with a  $p < 0.05$ .

Outcome	Statistical Test
Birth before 34 Weeks of Gestation	Two-sided Z-Test (RR, 95% CI)
Time to Birth	Log-rank test (HR, 95% CI)
Birthweight	Multilevel model (mean $\pm$ SD)
Fetal / Neonatal Death	Two-sided Z-Test (RR, 95% CI)
Neonatal Morbidity	Two-sided Z-Test (RR, 95% CI)
Need for Hospitalization	Two-sided Z-Test (RR, 95% CI)
Days of Hospitalization	Two-sided Z-Test (RR, 95% CI)
Maternal Adverse Events	Two-sided Z-Test (RR, 95% CI)
Pessary Intolerance	Two-sided Z-Test (RR, 95% CI)
Vaginal Infections	Two-sided Z-Test (RR, 95% CI)

the complete data set for the secondary endpoints will be available after the last women enrolled in this study has given birth, so the analysis of these outcome parameter will be done right after this event.

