## **10. Data Management and Registry File**

Patient's participation in the study will be annotated into the medical history. The main investigator will perform a list with the participant's names, ID numbers and codes. He also will have a file with all the information referring to the study. All the data will be collected in a database that will be accessed worldwide. The randomisation will be done on a computer basis. Once entering in the website, if the patient fulfils the inclusion criteria, the computer generated list will randomise the patient to "pessary" or "control" group. The excluded patients will be also collected in the database. Every participating centre will have its own randomisation list, and it will be accessible with a username and password. The trial staff will ensure that the participants' anonymity is maintained. Only a participant ID number on the CRF and in the electronic database will identify the participants. All documents will be stored securely and only accessible by trial staff and authorized personnel. The study will comply with the Data Protection Legislation that requires data to be anonymized as soon as it is mandatory to do so.

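### Section 7.1 describes women by an outcome instead of by randomised arm, and adjusts for unnamed confounders on a scale that does not match the promised relative risk

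*Protocol*

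**What the plan says.** Section 4.2 gives the design as "Open Multicentre Randomized Controlled Trial, in parallel groups". Section 7.4 analyses every randomised woman, and section 10 adds: "Every participating centre will have its own randomisation list".

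Section 7.1 then sets out the methods in this order:

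- Description: "A descriptive analysis by preterm birth will be carried out".
- Testing: "Two-sided Z-tests will be used for comparing among exposure and outcomes groups per pregnancy".
- Adjustment, followed directly by the effect measure: "A multivariate logistic regression will be fitted to control for possible confounders. Relative risks and 95% confidence interval will be calculated for the outcomes".

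The outcome table in section 7.1 has ten rows. Eight carry the entry that begins "Two-sided Z-Test (RR, 95% CI". Time to birth has a log-rank test with a hazard ratio, and birthweight has a multilevel model. Logistic regression appears in no row.

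**The concern.** Three features do not fit a randomised comparison.

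1. **Description by outcome.** Preterm birth is a result of the trial. Tables split by it compare women who delivered early with women who did not, which is a risk-factor analysis. Followed as written, the section plans no description by allocated arm, so a reader could not judge baseline balance or see outcome counts per arm.

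2. **Adjustment for confounders.** Randomisation removes systematic confounding. Adjustment in a trial serves to gain precision from prognostic factors and to respect the factors used in randomisation. Separate lists per centre make centre such a factor, and an open-ended confounder model need not include it.

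3. **Scale and role of the adjusted result.** The logistic model reports an odds ratio unless something further is done with it. The section promises relative risks and does not say what the logistic model reports, for which outcomes it is fitted, or whether it or the Z-test gives the main estimate.

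The stake is interpretation. An unadjusted relative risk and an adjusted odds ratio cannot be compared directly: part of any difference comes from the change of scale, and part arises because an odds ratio shifts when a prognostic factor is added even if the arms are balanced. A reader could mistake either shift for an effect of adjustment.

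**Working it through.** **Inputs (Protocol section 7.2).** Treatment proportion p1 = 0.924, control proportion p2 = 0.80, two-sided alpha 0.05, power 80%, Z-test with pooled variance, 121 per group.

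**Step 1: reproduce the plan's figure.** With mean proportion (0.924 + 0.80)/2 = 0.862 and difference 0.124:

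n = [1.960 × √(2 × 0.862 × 0.138) + 0.842 × √(0.924 × 0.076 + 0.80 × 0.20)]² / 0.124²

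= [0.956 + 0.404]² / 0.01538 ≈ 120.3, rounded up to 121 per group.

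Power at 121 per group is 80.2%. The stated figure is reproduced, so these proportions are a sound basis for comparing the two scales.

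**Step 2: direction of the outcome.** Section 7.2 does not name the outcome. The higher proportion is in the treatment group, so it is taken here as a favourable outcome, in line with the primary outcome in section 4.1.1. The complement (0.076 versus 0.20) is the adverse event.

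**Step 3: both effect measures.** RR = p1/p2; OR = [p1/(1 − p1)] / [p2/(1 − p2)].

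| Scale | Proportions | RR | OR |
|---|---|---|---|
| Favourable outcome | 0.924 vs 0.80 | 0.924/0.80 = 1.155 | (0.924/0.076)/(0.80/0.20) = 12.16/4 = 3.04 |
| Adverse event | 0.076 vs 0.20 | 0.076/0.20 = 0.38 | (0.076/0.924)/(0.20/0.80) = 0.0823/0.25 = 0.33 |

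On the adverse-event scale this is a 62% reduction in risk (1 − 0.38) against a 67% reduction in odds (1 − 0.33). On the favourable scale the gap is large: a 15.5% relative increase in the proportion against a threefold increase in odds.

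**Step 4: design against analysis.** No arithmetic applies here. Section 10 randomises within centre. Section 7.1 names centre in none of its methods. The multilevel model for birthweight does not state its levels, so centre may or may not be one of them. The Z-tests, which cover eight of the ten rows, are described without strata.

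**The case against.** The strongest reply is that the text contains no contradiction. The table ties the relative risk to the Z-test, a crude relative risk follows directly from the two arm proportions, and no sentence derives it from the logistic model. A relative risk can also be obtained from a logistic model by marginal standardisation. This stands: the scale problem is one of ambiguity, and it matters only if the adjusted result supplies or accompanies the reported effect.

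The size of the gap is also open to challenge. The binary outcomes in the section 7.1 table are adverse events, and on that scale 0.38 and 0.33 are not far apart. This too stands. The figures 1.155 and 3.04 apply only to the favourable scale on which the sample size is stated.

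Four stronger readings are tempting, and the documents do not support them.

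- *That section 7.1 as a whole is a cohort plan.* Its table of Z-tests and a log-rank test suits a two-arm trial. Section 7.2 sizes a two-group comparison, section 4.10.3 refers to intention to treat, and section 7.4 keeps all randomised women.
- *That covariates will be picked by looking at the outcome.* The descriptive sentence and the regression sentence are not linked. The wording leaves room for this but does not plan it.
- *That the missing covariate list is itself an error.* Such a list is commonly left to a statistical analysis plan, which is not at hand, so its absence is not counted.
- *That the 22% versus 59% rates before 37 weeks in section 2.1 show the gap for this trial.* Those rates concern women with a short cervix compared with expectant management. This trial enrols on obstetric history, and section 4.4 gives progesterone to the control group. Birth before 37 weeks also has no row in the section 7.1 table.

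What remains is what section 7.1 actually states: description by an outcome, adjustment framed as confounder control, and two effect scales with no stated order between them. A later analysis plan would have to override that text, not merely add to it.

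**Conclusion.** The point holds in limited form and should be corrected before analysis. Section 7.1 describes women by preterm birth where a randomised trial calls for description by arm. It adjusts for open-ended confounders with a model whose natural output is not on the promised scale, and it does not say which result is the main one. No stated analysis names centre, although centre defines the randomisation lists.

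At the planning proportions the relative risk and odds ratio are 1.155 and 3.04 for the favourable outcome, and 0.38 and 0.33 for the adverse event. These figures assume that the section 7.2 proportions are a favourable outcome and its complement; rates for the other outcomes in the table are not given. The effect of leaving centre out cannot be quantified from the protocol, which gives neither the number of centres nor how much outcomes vary between them. Nothing here invalidates the unadjusted Z-test comparison or changes the sample size.

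**What to change.** Amend section 7.1 in three places.

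1. Present baseline characteristics and outcomes by randomised arm, and describe the Z-tests as comparisons between the two arms.
2. Name the unadjusted relative risk with its 95% confidence interval, from the Z-test comparison, as the main estimate for the binary outcomes.
3. Replace the confounder model with a supportive adjusted analysis on the relative-risk scale: either modified Poisson regression with robust standard errors, or marginal standardisation from the logistic model. Include centre and baseline prognostic factors known at entry, namely obstetric history and gestational age at randomisation. If a plain logistic model is kept, state that it reports an odds ratio and that it is supportive.

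The cost is a short amendment and a few lines of code. No new data are needed, and sample size and clinical conduct are unchanged. The one downside is that small centres may have to be pooled for the model to fit, so the pooling rule should be fixed in advance.

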### 4.1.2. Secondary outcomes:

[figure not shown]
- Offspring
  - Time to birth
    - Preterm birth before 37 weeks: rate of delivery before 36+6 weeks
    - Preterm birth before 34 weeks: rate of delivery before 33+6 weeks
    - Preterm birth before 32 weeks: rate of delivery before 31+6 weeks
    - Preterm birth before 30 weeks: rate of delivery before 29+6 weeks—
    - Preterm birth before 28 weeks: rate of delivery before 27+6 weeks—
  - Birth weight: median weight (g) of the newborns at birth
  - Fetal or neonatal death: rate of intrauterine demise or neonatal death during the first 24 hours
  - Neonatal morbidity: rate of major adverse neonatal outcomes before discharge from the hospital
    - Intraventricular Haemorrhage (IVH): grades III-IV
    - Retinopathy of prematurity
    - Respiratory Distress Syndrome (RDS): grades II-IV,
    - Need for ventilation > 72 h
    - Necrotising enterocolitis
    - Proven or suspected sepsis, antibiotics (>5 days)
    - Need (Duration in days) for neonatal special care (NICU)
  - Harm from intervention
- Mother:
  - Maternal death
  - Significant maternal adverse events (rate):
    - Heavy bleeding: bleeding that requires a medical intervention
    - Cervical tear: cervical rupture due to the pessary placement
    - Uterine rupture: rupture of the uterus due to contractions or surgery
  - Physical or psychological intolerance to pessary: discomfort or pain due to the pessary that makes daily life uncomfortable (number of cases)
  - Rupture of membranes before 32 weeks: rate of—rupture of amniotic membranes before 31+6 weeks
  - Infection/inflammation
  - Hospitalisation for threatened preterm labour before 32 weeks: requirement of hospitalisation due to preterm contractions that need medical treatment to try to stop them before 31+6 weeks (rate)

- Mean hospital stay duration: number of days of admittance at the hospital
- Use of tocolytic treatment: Type of tocolytic, days of treatment, dose

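### The Section 7.1 test table assigns a relative risk to two secondary outcomes that cannot have a valid one: a number of days, and intolerance of a device that only one arm receives

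*Protocol*

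**What the plan says.** Protocol Section 7.1 lists ten outcomes with a test and an effect measure for each. Eight of the ten carry the same entry, a two-sided Z-test with relative risk and 95% CI. Two of those eight matter here.

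- **Days in hospital.** The row reads "Days of Hospitalization Two-sided Z-Test (RR, 95% CI". Section 4.1.2 lists, under the mother, "Mean hospital stay duration: number of days of admittance at the hospital". It also lists, under neonatal morbidity, a duration in days for neonatal special care. The table does not say which of the two its row refers to. A separate row, "Need for Hospitalization", also carries a relative risk.
- **Intolerance.** The row "Pessary Intolerance" has the same entry. Section 4.1.2 defines this outcome as discomfort or pain caused by the pessary, and asks for a number of cases.

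The text above the table adds two general rules: "Relative risks and 95% confidence interval will be calculated for the outcomes", and "Statistical significance will be accepted in all cases" at p < 0.05. It also plans a descriptive analysis "calculating means and medians for quantitative variables and proportions for categorical variables".

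**The concern.** A relative risk is a ratio of two proportions. It needs an outcome that each woman either has or does not have, and one that women in both arms can have. The days row fails the first condition and the intolerance row fails the second.

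For days, a figure labelled as a relative risk, next to the row on need for hospitalization, could be taken for a risk of admission. The result a reader would want, the between-arm difference in days, is not planned.

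For intolerance, the significance rule in Section 7.1 would be applied to a comparison whose outcome is fixed by design. A handful of cases would count as a significant difference between arms, although women without a pessary cannot be intolerant of one. The informative quantity for the device under test is how often wearers do not tolerate it and how precisely that is known. The table gives no interval for it.

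**Working it through.** **Days: the passages side by side**

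1. Section 4.1.2 measures both candidate outcomes, maternal stay and neonatal special care, in days.
2. No section gives a cut-off that would turn days into a proportion.
3. The row cannot be a loosely named yes/no outcome, because need for hospitalization has its own row.
4. The table does not treat other quantitative outcomes this way. Birthweight gets a "Multilevel model" with mean and SD, and time to birth gets a hazard ratio.
5. RR cannot be read as a rate ratio here, because the text of Section 7.1 spells it out as relative risks.

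A Z-test comparing mean days is feasible at this sample size. Only the effect measure is wrong.

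**Intolerance: who can be a case**

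1. By definition (Section 4.1.2), a case is caused by the pessary.
2. The schedule in Section 6.2 marks pessary placement for the pessary group only.
3. Controls receive progesterone (Section 4.4), or usual management with rescue cerclage (Section 2.2). The rescue named in Section 4.10.4 is cerclage. No section gives a control woman a pessary.

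The control count is therefore c = 0 by design.

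**Intolerance: arithmetic**

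The arm size is 121 (Section 7.2). That figure reproduces from the plan's own inputs of 0.924 v 0.800, two-sided 5%, 80% power and pooled variance:

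n = [1.960·√(2·0.862·0.138) + 0.842·√(0.924·0.076 + 0.8·0.2)]² / 0.124² = 120.3, rounded up to 121.

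It serves below only as the arm size.

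Relative risk = (a/121)/(0/121), which is undefined for every a > 0. Its log-scale confidence interval is undefined as well.

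The pooled Z-test can still be computed: z = (a/121)/√[p(1−p)·2/121], with p = a/242.

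| Cases, pessary v control | z | p |
|---|---|---|
| 3 v 0 | 1.743 | 0.081 |
| 4 v 0 | 2.017 | 0.044 |
| 5 v 0 | 2.260 | 0.024 |

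Four cases thus meet the p < 0.05 rule. If the true rate among wearers were 5% or 10% (assumed; the protocol gives none), the chance of at least four cases in 121 is 86% or 99.9% (binomial).

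**Off-protocol pessary use in controls**

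Suppose k of the 121 controls wore a pessary and all wearers had the same intolerance rate r. The ratio of true rates is then r/(r·k/121) = 121/k. The last column assumes r = 5%.

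| k (assumed) | Ratio of true rates, 121/k | Chance of p < 0.05 |
|---|---|---|
| 2 | 60.5 | 81% |
| 5 | 24.2 | 75% |
| 10 | 12.1 | 65% |

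The relative risk can then be finite, but it mainly counts how many controls wore a pessary. With k = 5 and r = 5% there is still a 0.95⁵ = 77% chance of no control case, which leaves it undefined.

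**What the pessary group alone would show**

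Exact (Clopper-Pearson) 95% intervals for illustrative counts:

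- 4/121 = 3.3% (0.9% to 8.2%)
- 6/121 = 5.0% (1.8% to 10.5%)
- 12/121 = 9.9% (5.2% to 16.7%)

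**The case against.** Both outcomes are secondary, no decision in the protocol depends on either row, and the entry looks like one cell repeated down a column. A statistician would probably analyse days by means anyway, and an analysis plan that is not shown may correct the table. The low consequence stands. The appeal to an unseen plan does not, because the protocol is not silent here: it fixes a wrong measure for two named outcomes.

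A reader might infer more than the documents support, in four ways.

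- *That the Z-test on days is itself invalid.* It is not; only the relative risk is.
- *That the protocol plans no usable summary.* Section 4.1.2 asks for a number of intolerance cases, and Section 7.1 plans proportions, means and medians, although it describes that analysis as by preterm birth rather than by arm. What is absent is a confidence interval for the pessary-group proportion and a between-arm difference in days.
- *That these two rows are the only place where the problem can arise.* Section 4.1.2 ties cervical tear to pessary placement and counts special care in days. Both fall under composite rows, and the same error would arise if either were analysed on its own.
- *That skewed stays call for a bootstrap or a rank test.* Nothing in the protocol requires either, and the ordinary large-sample interval for a mean difference is adequate at about 121 per arm.

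**Conclusion.** The table is wrong as written in two cells, and the consequence is minor. For days, the relative risk has no meaning without a cut-off. This holds whichever of the two day-count outcomes the row refers to. For intolerance, the relative risk is undefined and the test is uninformative, with four cases in 121 enough for p < 0.05.

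The intolerance conclusion rests on controls receiving no pessary, which is what the protocol schedules. Off-protocol use would make the ratio computable in some trials but not meaningful. The 5% and 10% rates and the numbers of control wearers are assumptions that show size only; the conclusion does not depend on them.

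It would be tempting to read this as a flaw in the trial's main comparison. The documents do not support that: neither row enters the primary outcome or the sample size calculation.

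**What to change.** In the Section 7.1 table:

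- **Days of hospitalization:** replace the entry with the difference in mean days and its 95% CI (ordinary large-sample interval), and state whether the row means maternal stay or neonatal special care.
- **Pessary intolerance:** replace the entry with the number and proportion with exact 95% CI, pessary group only, no between-arm test. List any case from off-protocol pessary use in controls separately.

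In the text of Section 7.1, limit the sentence on relative risks to yes/no outcomes that can occur in both arms. If special-care days or cervical tear due to pessary placement is analysed on its own, treat it like days or like intolerance respectively.

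The cost is two table entries and one sentence. No new data are needed, and the primary analysis and the sample size do not change.

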#### 4.10. Selection and withdrawal of subjects

##### **4.10. 1 Inclusion criteria.**

- Women with a singleton pregnancy and a history of at least one previous preterm delivery before 34+0 weeks and/or a history of late abortion
- 12+0 -18+0 weeks of gestation
- Minimal age of 18 years
- Informed consent signature

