## **7.4. Selection of subjects to be included in each analysis.**

The analysis will include all the subjects that have been randomised.

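### The secondary endpoints are declared complete, and analysed, as soon as the last woman enrolled gives birth, although several are followed past birth and, on the literal wording, some women may still be pregnant.

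*Protocol*

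**What the plan says.** Protocol section 7.1, below the table of tests, says that "the complete data set for the secondary endpoints will be available after the last women enrolled in this study has given birth", and continues: "so the analysis of these outcome parameter will be done right after this event". This is a stated rule for when the secondary endpoints are complete and when they are analysed.

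Section 4.1.2 defines several of those endpoints over a period that starts at birth:
- "Neonatal morbidity: rate of major adverse neonatal outcomes before discharge from the hospital"
- "Need for ventilation > 72 h"
- fetal or neonatal death: "rate of intrauterine demise or neonatal death during the first 24 hours"
- also sepsis with more than 5 days of antibiotics, and the number of days in neonatal special care.

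The same list contains time to birth, preterm birth at five gestational thresholds, and birth weight.

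Section 4.10.1 admits women at "12+0 -18+0 weeks of gestation". Section 7.4 says: "The analysis will include all the subjects that have been randomised".

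No other section sets a later close. Section 4.10.3 follows women who stop treatment until delivery. The schedule in section 6.2 lists a postnatal evaluation without a date. Section 7.3, on completion of the trial, names only maternal death.

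**The concern.** An outcome counted up to discharge is not complete on the day of a birth. If the rule is followed as written, recent babies enter the analysis with truncated NICU days and with morbidity that has not yet had time to appear. These will often be preterm babies, who stay longest and carry most of the morbidity.

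The literal wording also ties the cut-off to one woman's delivery date. She is last in order of enrolment, and with a six-week entry window she need not be last to deliver. Women still pregnant then have no birth weight and may have no status at preterm thresholds they have not yet reached, although section 7.4 promises to analyse everyone randomised. The Z-tests on rates and the birth-weight model have no means of using such women. The log-rank test for time to birth can censor them.

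**Working it through.** The protocol attaches no figure to the trigger, so there is none to reproduce. The inputs from the protocol are the entry window of 12+0 to 18+0 weeks (section 4.10.1), the outcome definitions (section 4.1.2) and 242 women (section 7.2).

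**Step 1: outcomes that run past birth.** Take the reading kindest to the plan, in which the trigger is the last delivery in the whole trial. At that moment the triggering baby has been observed for 0 hours. The definitions need 24 hours (death), more than 72 hours (ventilation), more than 5 days (antibiotics), and the time to discharge (morbidity) or to the end of special care (NICU days). None is complete. This needs no assumption.

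**Step 2: order of delivery on the literal reading.** Suppose the last woman enrolled enters at 18+0 and delivers at G weeks. The trigger then falls G − 18 weeks after her entry. A woman who entered on the same day at 12+0 is at 12 + (G − 18) = G − 6 weeks. If that woman would deliver at 40+0, she needs 28 weeks from entry. A woman like her is therefore still pregnant at the trigger if she enrolled less than 28 − (G − 18) = 46 − G weeks before the last woman.

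| Last woman delivers (G) | Same-day 12+0 entrant is at | 12+0 entrant going to 40+0 still pregnant if enrolled within |
|---|---|---|
| 28 | 22 weeks | 18 weeks |
| 34 | 28 weeks | 12 weeks |
| 37 | 31 weeks | 9 weeks |
| 40 | 34 weeks | 6 weeks |

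No early delivery is needed: even at G = 40 the other woman has six weeks left.

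**Step 3: how many.** This needs accrual speed, the distribution of gestation at birth and length of stay. The protocol gives none of them, so these are assumptions. Two sets were simulated (4,000 runs, 242 women), both with uniform accrual and uniform entry over 12 to 18 weeks.
- Set A: about 14% of births before 34 weeks, spread over 24 to 34; the rest over 34 to 41.5, peaking at 39; babies born before 34 weeks in hospital until 37 weeks, others for 3 days.
- Set B: 20% preterm, spread over 24 to 37 weeks; term births around 39 weeks; preterm babies in hospital until 40 weeks.

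| At the trigger, accrual over 1 / 2 / 3 years | Set A | Set B |
|---|---|---|
| Median women undelivered | 5 / 2 / 1 | 5 / 2 / 2 (repeat run) |
| Mean women undelivered | 9.4 / 4.8 / 3.3 | 10.3 / 5.4 / 3.4 |
| 95th percentile | 43 / 21 / 15 | 47 / 24 / 15 |
| Runs with at least one undelivered | 83% / 75% / 67% | 83% / 75% / 68% |
| Mean babies still in hospital | 2.9 / 2.0 / 1.6 (all) | 2.7 / 1.5 / 1.0 (preterm) |

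The set A hospital counts include the triggering baby. The repeat run of set B used a standard deviation of 1.2 weeks for term births, also assumed. The mean lies well above the median because the upper tail arises when the last woman happens to deliver very early.

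If the trigger is instead the last delivery in the trial, no woman is undelivered, and set A leaves 1.4 / 1.3 / 1.3 babies in hospital on average, including the triggering one.

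**The case against.** The sentence can be read charitably. It speaks of a complete data set, section 4.10.3 follows women to delivery, section 7.4 analyses all randomised, and section 6.2 lists a postnatal examination. Taken together, the authors may simply have meant that analysis waits until the last births are in. On that reading the point about undelivered women falls away. It stands only on the literal wording. The point about outcomes after birth stands on either reading.

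The size is also modest. A woman past 34 weeks at the cut-off already has a known status for birth before 34 weeks. In the repeat run of set B, the number undelivered and still under 34 weeks had a median of 0 at every accrual length and was zero in 78% to 82% of runs. The births before 34 weeks that were missed averaged 0.20 / 0.10 / 0.08 per trial. That outcome is barely touched; birth weight and the 37-week threshold are more exposed.

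Three stronger readings are tempting, and the protocol does not support them.
- A reader might infer that the primary outcome is cut off too. The sentence names only the secondary endpoints and sets no trigger for the primary one.
- A reader might set the undelivered women against about 24 expected control-arm events (20% of 121). That compares women from both arms with events in one, an undelivered woman is not a lost event, and section 7.2 does not say what its proportion of 0.80 measures.
- A reader might conclude that the treatment comparison is biased. The cut-off is a calendar date common to both arms, and no between-arm bias has been shown.

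**Conclusion.** The rule in section 7.1 is wrong as written for the secondary outcomes that section 4.1.2 follows past birth. That conclusion rests on the definitions alone and holds however the trigger is read. On the literal wording it can also leave women undelivered, with birth weight and some preterm-birth statuses missing, against section 7.4.

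The number affected is probably small: typically a few of 242 women and about 1 to 3 babies, under assumed accrual of 1 to 3 years. It has a long upper tail, because it hangs on one woman's delivery date. These counts illustrate the rule and do not predict this trial. The defect is limited to the timing of the secondary analysis; it is worth correcting because the correction is so cheap.

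**What to change.** Replace the closing sentence of section 7.1 with: *The secondary endpoints will be analysed after every randomised woman has delivered and every liveborn child has been discharged from hospital or has died.*

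This removes both problems and agrees with sections 4.1.2 and 7.4. It adds no visits, since the outcomes are already defined up to discharge, and it changes no treatment or clinical rule. The cost is a delay of some weeks to a few months before the secondary analysis, depending on the last deliveries and the longest neonatal stay.
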